## 1. Protocol Synopsis

Study Title	Baseline Controlled Study to Evaluate the Safety and Efficacy of Combined EMS and RF Treatments for Non-Invasive Circumference Reduction and Skin Tightening
Protocol No	DO608715A, Rev. 02
Sponsor	InMode Ltd.
Investigational Product	Evolve (InMode EmBody System) with Tite (Embody Plus Handpiece K183450) and Tone Applicators
Study Design	Prospective, open label clinical study.
Study Sites	[name] [name]
Patient Population and Sample Size	Subjects aged 18-65, healthy adults, seeking for non-invasive abdominal circumference reduction and skin tightening, male and females.  Approximately 20 healthy adult volunteers (10 per site), seeking for non-invasive abdominal circumference reduction, male and females, 18 to 65 years of age from up to 2 investigational sites.
Study Duration	Eligible subjects will receive up to 3 bi-weekly treatments (once in 2 weeks) with the Evolve device utilizing the Tite and Tone applicators according to the study protocol.  Study duration for each subject is approximately 8 months (including screening, up to three treatments and 3 follow-up visits at 1 months, 3 months and 6 months post last treatment.  Overall study duration will be approximately 14 months, depending on the subject recruitment rate.
Primary Objectives	The objective of this trial is to evaluate the safety and efficacy of the Evolve device utilizing the Tite and Tone applicators for abdominal non-invasive circumference reduction and skin tightening
Secondary Objective	The secondary objective of this study is subject satisfaction, as measured with a self-assessment questionnaire and a rating of device and procedure related adverse events.

Endpoints	
Primary Effectiveness Endpoint:
 
 
The primary efficacy endpoint in this trial is the statistical difference of circumference reduction between Control (baseline measurement) and three points of follow-up measurement: 4 weeks (1Month) 12 weeks (3Month) and 24 weeks (6 months) following the last Tx session. The primary effectiveness endpoint will be calculated based on those patients whose weight remains stable during the study period. A subject is defined as having maintained her weight during the treatment period if it remained within <math>\pm 3\%</math> (inclusive) of baseline for the respective period.
 
Improvement in in skin appearance comparing pre and at 1, 3 months and 6 months post last treatment photographs (as assessed by blinded investigators): 
 
Success is defined by correct identification of the pre and post treatment photos as demonstrated in at least 70% or greater of patients completed the treatment at 1 month, 3 months and 6 months post treatment.
 
At least 2 out of 3 blinded evaluators should agree on the assessment.
 
 
 
Optional: 3D Photographic analysis will be conducted using QuantifiCare System at 1 month, 3 months and 6 months follow up visits and compared to the baseline.
 
Investigator assessment of the skin appearance improvement comparing pre and post treatment using 0 - 4 -points Likert scale at 1 month, 3 months and 6 months follow up visits: 4 = Significantly marked improvement; 3 = Marked improvement; 2 = Moderate improvement; 1 = Slight improvement; 0 = No difference
 
 
Primary Safety Endpoint
 
Safety Endpoint Rate of all device and procedure related adverse events (AE's) and serious adverse events (SAE's) occurring during the study.
 
Secondary Effectiveness Endpoints:
 
Subject satisfaction and comfort:
 
 
Improvement assessment will be performed independently by the subject himself using 4 points Likert scale questionnaire (Global Aesthetic Improvement Scale), as follows: 
 
4 = Significantly marked improvement; 3 = Marked improvement; 2 = Moderate improvement; 1 = Slight improvement; 0 = No difference.
 
 
 
Subject assessment of satisfaction will be filled out by subjects using a 5-points Likert scale, as follows: 
 
+2 = Very satisfied; +1 = Satisfied; 0 = Indifferent; -1 = Disappointed; -2 = Very disappointed.
 
 
 

------------------	--

	Baseline Controlled Study to Evaluate the Safety and Efficacy of Combined EMS and RF Treatments for Non-Invasive Circumference Reduction and Skin Tightening	
	Protocol No: DO608715A    SIRB ID: 7398	Rev. Date: Sep 19, 2019

	
 
• Subject assessment of comfort will be filled out by subjects using a 5-point Likert scale, as follows: 
 
- +2 = Very comfortable; +1 = Comfortable; 0 = Indifferent; -1 = uncomfortable; -2 = Pain.
 
 
 

--	--

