## 2. Data analysis

### 9.1 Analysis Sets

- Safety Analysis Set

The safety analysis set will include all subjects using Embrace procedures at least a single time.

- Performance Analysis Set

Performance analysis set will consist of all subjects providing at least one post treatment performance measurement.

- Treatment of Missing Values

Only observed data will be used; i.e. missing data will not be imputed.

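### The 70% photo-identification rule carries no weight condition, although the circumference endpoint beside it is restricted to weight-stable subjects

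*Combined protocol and SAP*

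**What the plan says.** All the endpoint text is in section 1, Protocol Synopsis, Endpoints, under the primary effectiveness heading.

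- **Item 1 (circumference).** "The primary effectiveness endpoint will be calculated based on those patients whose weight remains stable during the study period". Stability is then defined: "A subject is defined as having maintained her weight during the treatment period if it remained within" ±3% of baseline, limits included.
- **Item 2 (blinded photographs).** "Success is defined by correct identification of the pre and post treatment photos", to be shown in "at least 70% or greater of patients completed the treatment at 1 month, 3 months and 6 months post treatment". Scoring is by majority: "At least 2 out of 3 blinded evaluators should agree on the assessment". Weight is not mentioned.
- **Items 3 and 4 (optional 3D analysis; investigator's 0 to 4 rating).** No population is named and weight is not mentioned.

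Section 9.1 defines a further set: "Performance analysis set will consist of all subjects providing at least one post treatment performance measurement". It also says "Only observed data will be used; i.e. missing data will not be imputed". Section 9.2 specifies means, standard deviations and paired t-tests. It contains no adjustment, subgroup or listing by weight.

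**The concern.** The plan itself treats a weight change beyond 3% as a reason not to credit the device with a circumference change. A subject outside that band is dropped from item 1. At the same visit the same subject stays in item 2 and counts as a success if at least two of the three evaluators pick out the later photograph.

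Two features of the design make this matter. The study is open label and baseline is its only control, so nothing else separates a device effect from a change in weight. And although item 2 is introduced as skin appearance, what is scored is which photograph came first, not a graded skin change. Blinding the evaluators does not remove the cue: a slimmer or a fuller abdomen is visible to someone who does not know the order. Subjects come to the study wanting a smaller abdomen and are followed to 6 months after the last treatment, so some weight change is plausible.

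At stake is what a met 70% bar can be said to show. It would look like independent support for the circumference result, while part of it could come from subjects whom the circumference analysis sets aside.

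**Working it through.** The plan gives no sample-size, power or error-rate figure for the 70% rule, so there is none to reproduce. The gap is textual. The arithmetic only shows how far weight-changers could move the result.

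**Inputs from the documents**
- Planned N: about 20 (Protocol Synopsis).
- Threshold: 70% of completers (item 2), so 0.70 × 20 = 14 correct if all 20 complete.
- Scoring: majority of three evaluators (item 2).

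**Assumptions (not in the documents)**
- All 20 complete, and subjects are independent.
- Weight-stable subjects are identified at p0 = 0.5. If each of three independent evaluators guesses at 0.5, the majority is right with probability 3(0.5)²(0.5) + (0.5)³ = 0.5.
- k subjects are outside ±3%, in either direction, and are identified with probability p1.

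**Formula**

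P(pass) = Σₓ P[Bin(k, p1) = x] × P[Bin(20 − k, 0.5) ≥ 14 − x], for x = 0 to k.

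**Worked case, k = 4, p1 = 0.90**
- x = 4: 0.6561 × P[Bin(16, 0.5) ≥ 10] = 0.6561 × 0.2272 = 0.1491
- x = 3: 0.2916 × P[Bin(16, 0.5) ≥ 11] = 0.2916 × 0.1051 = 0.0306
- x = 2: 0.0486 × P[Bin(16, 0.5) ≥ 12] = 0.0486 × 0.0384 = 0.0019
- x = 1 and x = 0 together: less than 0.0001
- Sum: 0.182

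**Results, one visit, 14 of 20 needed**

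| Weight-changers k | p1 = 0.75 | p1 = 0.90 | p1 = 0.95 | p1 = 1.0 |
|---|---|---|---|---|
| 0 | 0.058 | 0.058 | 0.058 | 0.058 |
| 1 | 0.071 | 0.078 | 0.081 | 0.084 |
| 2 | 0.086 | 0.105 | 0.112 | 0.119 |
| 4 | 0.125 | 0.182 | 0.204 | 0.227 |
| 6 | 0.176 | 0.294 | 0.343 | 0.395 |

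The denominator stays at 20 throughout, so the rise down each column is due to the weight-changers alone. If four weight-changers are all identified, 14 − 4 = 10 of the 16 weight-stable subjects (62.5%) are enough.

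**Why the two denominators are not compared directly.** In 16 weight-stable subjects, 70% is 11.2, so 12 are needed and the effective bar is 12/16 = 75%. With p1 = p0 = 0.5 and k = 4, so no weight effect at all, the completer rule passes with probability 0.058 and the weight-stable rule with 0.038. That gap is rounding, not confounding.

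**Three visits.** Item 2 names 1, 3 and 6 months. If all three must pass, the per-visit figures are upper bounds. If visits were independent, 0.182 to 0.204 would become 0.182³ to 0.204³ = 0.006 to 0.008. Visits on the same subjects will be correlated, so the joint figure should lie between that and the single-visit value.

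**The case against.** The strongest reply is that the plan does not contradict itself. The weight sentence sits inside item 1, straight after the primary endpoint has been described as circumference reduction, and most naturally refers back to that. Item 2 is a separate endpoint with its own stated denominator, and different endpoints may use different populations. This stands. Because the weight sentence repeats the wording of the heading, a reader might infer that the block gives two conflicting populations to one endpoint, and that the same data can yield opposite decisions. For example, 15/20 = 75% passes in completers while 10/15 = 66.7% fails in the weight-stable. That inference needs item 1 to override item 2's explicit denominator, which the text does not support. What remains is a loosely worded reference worth tightening.

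Second, a reader might infer that the trial has no protection from weight change at all. The available text is a synopsis and a short analysis section, without eligibility, diet or photography procedures. It supports only the narrower statement that these sections give no weight condition, adjustment or display for items 2 to 4.

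Third, the number of weight-changers and their identification rate are assumed. With one weight-changer identified at 90%, the chance of passing is 0.078 against 0.058, which is small. This also stands, and the table therefore shows a range.

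None of this removes the main gap: a subject set aside for weight in item 1 can count as a success in item 2, and nothing in the available text would show it.

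**Conclusion.** The point holds as a gap in how the photo endpoint can be interpreted. Item 2's completer denominator is legitimate, but with baseline as the only control and success scored as pre/post identification, weight change in either direction can contribute to meeting the 70% bar.

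In the illustration, two weight-changers among 20 roughly double the single-visit chance of passing by guesswork (0.058 to between 0.105 and 0.112), and four roughly triple it (to between 0.182 and 0.204). This assumes 20 completers, independent subjects, guessing at 50% in weight-stable subjects and 90 to 95% identification in weight-changers. Requiring all three visits lowers every figure. The textual gap depends on none of these numbers.

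A reader might go further and infer that photo success should count only if the bar is met both in completers and in weight-stable subjects. The documents do not call for that. It would be a design choice, and it would turn a selection on post-baseline weight into a second hurdle in an already small sample. A supportive analysis, a table and a limit on the claim are proportionate: an inexpensive improvement rather than repair of an invalid endpoint.

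**What to change.** 1. In item 1, change the subject of the weight sentence to *the circumference endpoint*, so that it cannot be read as covering items 2 to 4.
2. In item 2, keep the completer denominator for the 70% rule. Pre-specify, as a supportive analysis, the same calculation at each visit in subjects within ±3% of baseline weight at that visit.
3. Tabulate items 2 to 4 (item 3 if done) by weight status at each visit: lost more than 3%, within ±3%, gained more than 3%. Gainers need their own row because a gain can also reveal the order of the photographs.
4. State that if the 70% bar is met only with weight-changers included, the photo result will not be presented as evidence of a device effect independent of weight.

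**Cost.** Protocol and SAP wording and one extra table. Item 1 already needs weight relative to baseline, so no new visits, evaluators or procedures follow. The weight-stable denominator will be smaller and less precise, and it is selected on a post-baseline measurement. That is why it should support the completer result rather than replace it.

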### 9.2 Statistical Analysis

Means, and standard deviations for each characteristic will be calculated. Paired sample t-test will be computed to assess changes in before treatment and follow-up scores. Statistical significance will be calculated and two-tail significance level of 0.05 will be used. All analyses will be conducted using IBM SPSS 21.0.

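### The two improvement scales have no category for worsening, so their scores are biased upward whenever any subject looks worse

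*Combined protocol and SAP*

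**What the plan says.** The Endpoints section of the Protocol Synopsis defines two improvement ratings.

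- Primary effectiveness item 4, at 1, 3 and 6 months: "Investigator assessment of the skin appearance improvement comparing pre and post treatment using 0 - 4 -points Likert scale", with the levels "4 = Significantly marked improvement; 3 = Marked improvement; 2 = Moderate improvement; 1 = Slight improvement; 0 = No difference".
- Secondary effectiveness: "Improvement assessment will be performed independently by the subject himself using 4 points Likert scale questionnaire (Global Aesthetic Improvement Scale", with the same five levels. Five levels are listed under a four-point label.

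The other two subject-rated scales have negative levels. Satisfaction starts at plus two: "2 = Very satisfied; +1 = Satisfied; 0 = Indifferent; -1 = Disappointed; -2 = Very disappointed". Comfort does too: "2 = Very comfortable; +1 = Comfortable; 0 = Indifferent; -1 = uncomfortable; -2 = Pain".

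The design is given as "Prospective, open label clinical study", with about 20 subjects and baseline as the control. Section 9.1 analyses observed data only, without imputation. Section 9.2 calls for means and standard deviations and adds "Paired sample t-test will be computed to assess changes in before treatment and follow-up scores", two-sided at 0.05. The documents give no scoring rule for a worsened appearance, and no null value, success threshold or dedicated analysis for the two improvement ratings.

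**The concern.** A scale that stops at no difference cannot represent a subject whose skin looks worse. The rater's only choices are 0, which merges that subject with the unchanged, or a blank, which removes the subject from the summary. Both push the mean up.

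In a randomised comparison the same floor would apply to both arms and the contrast would partly absorb it. Here there is no concurrent arm, so the score has nothing beside it to show how much of it comes from the floor. A mean above zero could then look like evidence of benefit when better and worse ratings are equally common. Mild cosmetic worsening that nobody reports as an adverse event would be lost, and it could not be recovered later from a score of 0.

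**Working it through.** The plan states no figure for these scales, so there is none to reproduce. The check has two parts: the bias in the mean, which needs no test, and the consequence if a test were applied.

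**Inputs from the documents.** Levels 0 to 4 on both scales (Synopsis, Endpoints); n about 20 (Synopsis); blanks not imputed (9.1); two-sided 0.05 (9.2).

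**Inputs assumed.** A proportion a of subjects is truly one category better, a proportion b one category worse, and the rest unchanged. The documents give neither rating variability nor a rate of worsening, so a range is shown.

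**1. Bias in the mean.**

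- True mean = a - b.
- Recorded mean if worse is rated 0 = a. Bias = a - (a - b) = b.
- Recorded mean if worse is left blank = a / (1 - b).

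With a = b = 0.20, the true mean is 0. Rated 0, the recorded mean is 0.20. Left blank, it is 0.20 / 0.80 = 0.25, and the share rated improved also rises from 20% to 25%. The bias is zero only if b = 0.

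**2. Consequence if scores were tested against 0.** Here worsening is recorded as 0 and a one-sample t-test against 0 is used. This equals a paired t-test only if every baseline value is taken as 0.

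With k subjects rated 1 and the rest rated 0, the mean is m = k/n, SD = sqrt[ n/(n-1) × m(1-m) ], and t = m / (SD/sqrt(n)).

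- n = 20, k = 4: m = 0.20, SD = 0.410, SE = 0.0918, t = 2.18, p = 0.042.
- n = 20, k = 3: m = 0.15, SD = 0.366, SE = 0.0819, t = 1.83, p = 0.083.
- Four ratings of 1 also suffice at n = 15 (p = 0.041) and n = 10 (p = 0.037); three do not (p = 0.082 and 0.081).

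The test therefore rejects when at least four subjects score 1, and the rejection probability is P(X ≥ 4) for X ~ Binomial(n, a). With a = b, so that the true net change is zero:

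| Better / worse | n = 20 | n = 15 | n = 10 |
|---|---|---|---|
| 5% / 5% | 1.6% | 0.6% | 0.1% |
| 10% / 10% | 13.3% | 5.6% | 1.3% |
| 20% / 20% | 58.9% | 35.2% | 12.1% |
| 30% / 30% | 89.3% | 70.3% | 35.0% |

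**3. Comparison with a two-sided scale.** Scoring the same subjects -1, 0 or +1 and enumerating exactly at n = 20, the two-sided rejection rate is 1.4%, 4.4%, 4.5% and 5.4% for the four rows, half of it in the direction of benefit. Where the table shows inflation, it comes from the truncation.

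**The case against.** The strongest counter-argument is that the alarming figures depend on an analysis the plan does not state. Section 9.2 describes a paired test of before-treatment and follow-up scores, and an improvement rating has no before-treatment score. No null of 0 is stated for item 4. This stands: a reader might infer that the trial has a 59% false-positive rate on these scales, and the documents do not support that. The figure is conditional on an assumed test and on assumed proportions at full enrolment. At 5%/5% with n = 20, or 10%/10% with n = 10, the rate is below the nominal 5%.

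Three other stronger readings also go beyond the text.

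- That a worsened subject is scored 0 by rule. No section says so, and the rating could equally be left blank.
- That the mean rating will be taken directly as efficacy. Section 9.2 says means are calculated, but no section says how item 4's mean is to be interpreted.
- That the scales conceal safety information. Device- and procedure-related adverse events are the primary safety endpoint, so harm has its own channel. What is lost is narrower: mild cosmetic worsening not reported as an adverse event.

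It is also fair to say that these are not the only efficacy measures. Circumference can move either way, the blinded photograph identification has its own 70% criterion and can fail, and satisfaction and comfort have negative levels. This limits the weight of the point in the trial as a whole but does not repair the two scales. Photograph identification asks which picture is before and which after, not how far the skin improved or worsened.

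**Conclusion.** The point holds for the two improvement ratings and no others. Their anchors leave a worsened subject without a valid answer, and whether that subject is rated 0 or left blank, the mean and the distribution of ratings shift upward. With worsening of one category rated as 0, the bias in the mean equals the proportion who worsen.

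The size in this trial is unknown, because the documents give no rate of worsening or rating variability. The rejection rates, from about 2% to 89% at n = 20 and lower with fewer evaluable subjects, illustrate what would follow if worsening were recorded as 0 and scores were tested against 0. They are not properties of the stated plan. If the scores are only summarised, there is no formal type I error and the upward bias is the whole of the finding. It is still worth correcting, because one of the scales is listed among the primary effectiveness measures and the study has no concurrent comparison.

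**What to change.** Add worse categories to both scales that mirror the improvement categories. Report the full distribution at each visit, including the proportion rated worse, and not the mean alone. Do not use a test of the truncated score against 0 as evidence of benefit. While the item is open, make the four-point label on the subject scale agree with its number of levels.

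The cost is a change to two questionnaire items, with no extra visits or subjects. Under the Statement of Compliance it needs sponsor agreement and documented IRB approval. It is best made before the scales are first used, so that two versions are not mixed; the documents do not say whether enrolment has begun. The mean rating may come out slightly less favourable. The change does not remove expectation bias: the study is open label, and item 4, unlike the photograph identification, does not state that the rater is blinded.

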## Statement of Compliance

This study will be conducted in accordance with the Code of Federal Regulations on the Protection of Human Subjects (45 CFR Part 46), any other applicable US government research regulations, and institutional research policies and procedures. The Principal Investigator will assure that no deviation from, or changes to the protocol will take place without prior agreement from the sponsor and documented approval from the Institutional Review Board (IRB), except where necessary to eliminate an immediate hazard(s) to the trial participants.

## 2. Data analysis

### 9.1 Analysis Sets

- Safety Analysis Set

The safety analysis set will include all subjects using Embrace procedures at least a single time.

- Performance Analysis Set

Performance analysis set will consist of all subjects providing at least one post treatment performance measurement.

- Treatment of Missing Values

Only observed data will be used; i.e. missing data will not be imputed.

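### Observed-only paired t-tests and an unclear photo denominator leave the primary effectiveness results dependent on who returns, with no model or sensitivity analysis to show how much

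*Combined protocol and SAP*

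**What the plan says.** **Missing data and test.** Section 9.1 (Analysis Sets) says "Only observed data will be used; i.e. missing data will not be imputed". It defines the Performance Analysis Set as every subject with one or more post-treatment performance measurements. Section 9.2 names a single test: "Paired sample t-test will be computed to assess changes in before treatment and follow-up scores", at a two-sided level of 0.05.

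**Circumference endpoint.** The synopsis compares baseline with "three points of follow-up measurement: 4 weeks (1Month) 12 weeks (3Month) and 24 weeks (6 months) following the last Tx session". It adds a restriction: "The primary effectiveness endpoint will be calculated based on those patients whose weight remains stable during the study period".

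**Photo endpoint.** Success means that the pre- and post-treatment photographs are correctly identified in "at least 70% or greater of patients completed the treatment at 1 month, 3 months and 6 months post treatment".

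**Size and length.** The synopsis plans "Approximately 20 healthy adult volunteers (10 per site", from up to two sites, and says "Study duration for each subject is approximately 8 months".

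The text supplied gives no expected dropout, no longitudinal model, no sensitivity analysis for missing data and no rule for a missing photo pair.

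**The concern.** Section 9.2 does not say in so many words that there will be one test per visit. It follows, though, from a paired test, three follow-up points and no repeated-measures model. A subject who attends at 1 and 3 months but misses 6 months stays in the Performance Analysis Set and contributes nothing to the 6-month comparison, although the earlier results say something about the missing one. The three comparisons may then rest on three different groups of people, and an apparently durable effect could partly reflect who came back.

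The study is open label and compared only with baseline, so no control arm shares such a distortion. Volunteers seeking a cosmetic result who see none may be less inclined to return. That is plausible, but the documents do not establish it.

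The photo endpoint is a pass/fail rule on a small sample, so one or two subjects in or out of the denominator can change the result. The denominator could be subjects who finished the treatment sessions, subjects who finished follow-up, or (by section 9.1) subjects with any post-treatment measurement.

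**Working it through.** **Inputs from the documents:** about 20 subjects (2 × 10), a 70% photo threshold, three follow-up points, observed data only, paired t-test. **Assumptions, because the documents give no figure:** dropout rates and their relation to response, a between-visit correlation of 0.7, a circumference-change SD of 2.5 cm where centimetres are quoted, and true photo identification rates. The planned number comes without power, effect size or SD, so apart from 2 × 10 = 20 there is no sample-size figure to reproduce.

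**1. Photo rule.** With n pairs available, the smallest passing count is the smallest r with r/n ≥ 0.70. The same r is then taken over all 20.

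| Missing | Needed | Observed-only | Over all 20 |
|---|---|---|---|
| 0 | 14 | 14/20 = 70% | 70%, pass |
| 1 | 14 | 14/19 = 73.7% | 70%, pass |
| 2 | 13 | 13/18 = 72.2% | 65%, fail |
| 4 | 12 | 12/16 = 75% | 60%, fail |
| 6 | 10 | 10/14 = 71.4% | 50%, fail |

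One missing subject changes nothing. From two on, the choice of denominator can decide the result.

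**2. Circumference shift at 6 months.** Let the chance of loss be a in the lower half of earlier response and b in the upper half, and let ρ be the correlation between visits. The mean of a standard normal variable in its upper half is √(2/π) = 0.798. The shift in the observed 6-month mean, in SD units, is

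ρ × 0.798 × (a − b) / (2 − a − b).

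- a = 20%, b = 10%: 0.7 × 0.798 × 0.1/1.7 = 0.033 SD
- a = 30%, b = 10%: 0.7 × 0.798 × 0.2/1.6 = 0.070 SD
- a = 40%, b = 10%: 0.7 × 0.798 × 0.3/1.5 = 0.112 SD
- a = b: 0

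At an SD of 2.5 cm, the largest of these is 0.112 × 2.5 = 0.28 cm. With 15 of 20 observed, the standard error is 2.5/√15 = 0.65 cm, so the shift is about 0.43 of a standard error.

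**3. Effect on the t-test.** With no true change and N = 20, simulation of the 40%/10% case gives a significant result in the favourable direction in about 6% of trials. The figure is about 2.5% with complete data or with loss unrelated to outcome.

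**4. What a longitudinal model recovers.** In the same 40%/10% simulation, likelihood estimation that uses the earlier visit cuts the shift from about 0.11 SD to about 0.001 SD. If loss depends instead on the unseen 6-month value, the shift falls only by about half, from about 0.16 to about 0.08 SD.

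**5. Cost of counting missing pairs as failures.** N = 20, 14 needed, loss unrelated to outcome; exact binomial pass probabilities:

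| True rate | Loss | Complete data | Observed-only | Missing = failure |
|---|---|---|---|---|
| 80% | 10% | 91% | 86% | 68% |
| 80% | 20% | 91% | 84% | 38% |
| 70% | 20% | 61% | 52% | 15% |

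**The case against.** A reader might infer that the plan uses a completers-only denominator that turns a failed photo endpoint into a success. The documents do not support that, for two reasons.

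First, the denominator wording may refer to the treatment sessions, which the synopsis describes separately from the follow-up visits. On that reading, a subject who finishes the sessions and misses the 6-month photograph belongs in the denominator, with no stated way to be counted. The wording is unclear; it is not plainly a follow-up-completer rule.

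Second, 13/20 or 12/20 is a failure only if every missing subject is scored as one. Under loss unrelated to outcome, the observed-only rule does not inflate the pass rate: at a true rate of 60% and 20% loss it passes about 22% of the time, against 25% with complete data. Inflation needs outcome-related loss. With 30% loss among non-successes and 10% among successes, the observed-only pass rate is 38%.

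It can also be said that the circumference shift is small beside its standard error, and that the no-imputation sentence is not itself an error. Both are right. A mixed model uses observed data only and complies with that sentence; the weakness is pairing the sentence with a t-test that discards partial follow-up.

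Finally, only the synopsis and data analysis sections are available, so a rule for withdrawals elsewhere in the full protocol cannot be excluded.

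What remains is that earlier visits go unused, the photo denominator is undefined, and no sensitivity analysis shows whether loss matters.

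**Conclusion.** The concern holds in a limited form. As written, each circumference comparison depends on who has data at that visit, and the plan ignores earlier results that could correct part of any selective loss. Under outcome-related loss with an assumed correlation of 0.7, the 6-month change is too favourable by about 0.03 to 0.11 SD over the range examined. Under unrelated loss there is no bias, only less precision. For the photo endpoint, the firm result is arithmetic: with about 20 subjects and a 70% threshold, two missing subjects make the choice of denominator decisive.

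The documents do not show that loss will be related to response, so the plan cannot be said to produce a false success; it leaves that possibility unexamined. The change should be made because it is cheap and can be fixed before the data are seen.

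**What to change.** **Circumference.** Replace the separate t-tests with one repeated-measures mixed model for change at 1, 3 and 6 months. Include visit, site and baseline circumference, use an unstructured covariance, and fit it to all observed visits. Apply the weight-stability restriction as the plan defines it, and say explicitly which subjects and visits it leaves in the model. Keep the paired t-tests as a sensitivity analysis. State the limits: the model removes bias explained by earlier visits, but not bias from loss driven by the unseen result or from subjects with no follow-up at all.

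**Photo endpoint.** Name one denominator, consistent with the Performance Analysis Set, and say how a subject without a usable pair at a visit is handled. Add a sensitivity analysis over all treated subjects in which a missing pair counts as not correctly identified. This should not be the primary rule: when loss is unrelated to outcome, it lowers the pass probability far more than the observed-only rule does.

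**Reporting.** Give the number of subjects contributing at each visit.

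**Cost.** SAP wording and modest extra analysis; no additional subjects or visits. The sensitivity percentage can be well below the observed one: with 4 of 20 missing, 12/20 = 60% against 12/16 = 75%.
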